8.4.2 UNANTICIPATED PROBLEM REPORTING

The site primary investigators will report unanticipated problems (UPs) to the reviewing MGH and UCSD IRBs and to NIMBLE leadership. The UP report will include the following information:

- Protocol identifying information: protocol title and number, PI’s name, and the site IRB project number;
- A detailed description of the event, incident, experience, or outcome;
- An explanation of the basis for determining that the event, incident, experience, or outcome represents an UP;
- A description of any changes to the protocol or other corrective actions that have been taken or are proposed in response to the UP.

To satisfy the requirement for prompt reporting, UPs will be reported using the following timeline:

- UPs that are serious adverse events (SAEs) will be reported to MGH and UCSD IRBs and to the NIMBLE leadership within 24 hours of the investigator becoming aware of the event.
- Any other UP will be reported to MGH and UCSD IRBs and to the NIMBLE leadership within 72 hours of the investigator becoming aware of the problem.

An investigator shall submit to the sponsor and NIMBLE Leadership and to the site IRB a report of any unanticipated adverse device effect occurring during ultrasound scans as soon as possible, but in no event later than 10 working days after the investigator first learns of the effect (21 CFR 812.150(a)(1)), A sponsor who conducts an evaluation of an unanticipated adverse device effect under 812.46(b) shall report the results of such evaluation to the Food and Drug Administration (FDA) and to all reviewing

IRBs and participating investigators within 10 working days after NIMBLE consortium first receives notice of the effect. Thereafter the sponsor or designee (i.e. NIMBLE Leadership) shall submit such additional reports concerning the effect as FDA requests (21 CFR 812.150(b)(1)).

8.4.3 REPORTING UNANTICIPATED PROBLEMS TO PARTICIPANTS

Any UP regarding research participants' health (i.e. SAE) will be reported to participant in 24 hours. UP management strategies and next steps will be explained by site PI.

9 STATISTICAL CONSIDERATIONS

9.1 STATISTICAL HYPOTHESES

- Primary Efficacy Endpoint(s):
Different-day, different-operator reproducibility coefficient of ultrasound measures
- Secondary Efficacy Endpoint(s):
Same-day, same-operator repeatability coefficient of ultrasound measures;
Different-scanner, same-day reproducibility coefficient of ultrasound measures;
Precision and other metrics measured by investigational analyses of ultrasound measures; and
Vendor- or device-specific metrics of ultrasound measures

9.2 SAMPLE SIZE DETERMINATION

The following assumptions were made in determining sample size for the primary study objective:

1. Repeat measurements on the same participant follow a normal distribution.
2. $RDC_{\text{diff-day, diff-operator}}$ is in the range of 20-30% (wCV of 7.2-10.8%).
3. A balanced design is planned (i.e. equal number of participants per scanner) where the following scenarios describe the possible RDCs across the five scanners:
 - 25, 25, 25, 25, 25%
 - 24, 25, 25, 26, 27%
 - 23, 25, 25, 27, 29%
 - 23, 25, 25, 27, 30%
4. A study with 80% power is desired.

The null hypothesis for the primary study objective is $H_0: RDC_{\text{diff-day, diff-operator}} \geq 35\%$, versus the alternative hypothesis that $RDC_{\text{diff-day, diff-operator}} < 35\%$, where RDC is the reproducibility coefficient for different day and different operator. The upper 95% confidence bound for the RDC will be constructed.

A Monte Carlo simulation study was conducted to determine the sample size needed. For each simulated participant, two observations were generated from a normal distribution with the specified variance. Samples of varying size were simulated. From each sample $RDC_{diff-day, diff-operator}$ was estimated, along with its 95% CI. This process was repeated 10,000 times.

In the table below the sample size is reported such that 80% of the samples of that size met the precision qualification (i.e. upper 95% confidence bound for $RDC < 35\%$). The results suggest that by pooling across the five scanners, up to 55 independent observations are needed. With each subject scanned on three different scanners at the two time points and assuming moderate correlation between observations from the same subject ($r=0.25$), we consider the design effect to account for the clustering of the data (i.e. 3 observations/subject). The design effect is $1+(s-1)r$, where r =correlation and s =# of observation/subject, i.e. $1+(3-1)0.25=1.5$. Thus, $(55 \times 1.5)/3=27.5$ so a study with 28 total participants would provide 80% power.

For estimating the $RDC_{diff-day, diff-operator}$ of VCTE, assuming an $RDC_{diff-day, diff-operator}$ of 25%, 32 subjects provides 80% power to show that the $RDC < 35\%$. Taking into consideration the possibility of a drop-out or technical failure rate of no more than 25%, a study with 40 total participants (20 per site) is proposed.

Number of Independent Observations needed for $\geq 80\%$ power as a function of the five scanners'

	$RDC_{diff-day, diff-operator}$			
RDCs across 5 scanners:	25, 25, 25, 25, 25%	24, 25, 25, 26, 27%	23, 25, 25, 27, 29%	23, 25, 25, 27, 30%
Total # independent observations	40	45	50	55

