Secondary endpoints:

- Evaluation of pooled same-day, same-operator repeatability coefficient of ultrasound-based measurements of SWS.
- Evaluation of pooled different-scanner, same-day reproducibility coefficient of ultrasound-based measurements of SWS.
- Evaluation of same-day, same-operator repeatability coefficient of VCTE on the measurement of SWS and Young's modulus.
- Evaluation of different-day, different-operator reproducibility coefficient of VCTE on the measurement of Young's modulus.

Exploratory endpoints

- Precision and other reliability metrics of vendor- or device-specific investigational measurements of other components of NAFLD such as steatosis and possibly inflammation.

Study Population

This study will enroll patients with suspected or confirmed diagnosis of NAFLD. Based on protocol-specified FIB-4 values, about one-third are expected to have low, one-third to have intermediate, and one-third to have high likelihood of advanced fibrosis. The sample size of 40 participants was determined to provide sufficient sample to provide >80% power to qualify SWS (or equivalent) as an ultrasound (US)-based biomarker for advancement to Stage 2. The threshold for automatic qualification for advancement to Stage 2 will be an upper bound of the 95% confidence interval (CI) of the reproducibility coefficient less than 35%. Dropouts and technical failures were included in this sample size determination.

Sex: ~ 50:50 – Note- no stratification will be done based on sex

Age: ≥ 18 yrs

Demographic group: Patients with a high probability of NAFLD based on the eligibility criteria

General health status: Patients with suspected or confirmed diagnosis of NAFLD

Geographic location: San Diego, CA and Boston, MA (greater metropolitan areas)

Phase

N/A

[figure not shown]
Description of Sites/Facilities Enrolling Participants Planned facilities/participating sites enrolling participants: University of California- San Diego (UCSD) and Massachusetts General Hospital (MGH)
 Number of sites: 2

Description of Study Intervention Study will not have any therapeutic intervention. The goal of the study will be evaluating the variability of ultrasound-based measures for the diagnosis and monitoring of NAFLD/NASH.

Study Duration 12 months

Participant Duration < 1 month

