Participants will be consecutively assigned to their corresponding category until the category is closed (reaches maximum of 11). Once a category is closed at a given site, participants will no longer be enrolled into that category at that site.

Each participant will undergo ultrasound imaging at Visit 1 (by operator 1) and at Visit 2 (by operator 2), separated by 1 to 7 days. The 7-day window for Visit 2 is selected to allow flexibility in scheduling while helping to ensure that there is no substantial biological change in the interim. Ultrasound exams at Visits 1 and 2 will be performed at about the same time of day (target is ± 2 hours) and with identical fasting and other preparation instructions. For each visit, each participant will be assigned to three of the five ultrasound scanners plus VCTE. As shown in the Schema (**Section 1.2**), for Visit 1, two of the three ultrasound exams will be repeated; the third ultrasound exam and the VCTE exam will be performed once. For Visit 2, the third ultrasound exam and the VCTE exam will be repeated; the other two ultrasound exams will be performed once. The selection of exams to be repeated will be based on a block assignment strategy to ensure an approximately equal number of scans are performed by each ultrasound system, in addition to VCTE. Thus, each subject will undergo a total of six exams at each of their two visits, for a total of 12 exams across both visits. For the repeated exams, subjects will get off the table with a short break (target about 5 minutes) before getting back on the table. Subjects will not be required to leave the room. The machine will not be turned off and powered up again to save time

Ultrasound operators will follow the acquisition procedures outlined in the imaging manual. The imaging manual will address patient positioning, image acquisition and quality control with scanning protocol input from the relevant ultrasound vendors. Additional investigational ultrasound data may be acquired, including with use of non-FDA-approved vendor proprietary software.

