5.5 STRATEGIES FOR RECRUITMENT AND RETENTION

Achieving target enrollment. It is not anticipated that there will be difficulty screening enough participants to meet the enrollment target of a total of 40 participants in this study. The goal will be to enroll approximately equal numbers of males and females, and to enroll a participant population representative of the sex, racial and ethnic mix of patients with NAFLD at the two clinical sites participating in this study. No special stratification will be done based on sex or race. Our effective screen-fail rate is expected to be up to about 25%, taking into account failure to satisfy inclusion and exclusion criteria, loss of participants due to possible uneven filling of our three enrollment categories, dropout, and technical failure. Thus, we expect to need to screen 50 participants to achieve our target enrollment of 40 participants.

Anticipated accrual rate. We anticipate being able to enroll one participant at each site every 2 weeks, and therefore expect to be able to complete enrollment in about 40 weeks.

Number of sites. There will be two clinical sites in this study (MGH and UCSD), and both have agreed to participate.

Source of participants. Participants at MGH will be recruited from EMR review and the Fatty Liver Disease Clinic. Participants at UCSD will be recruited from the UCSD NAFLD Research Center.

Methods of identification and approach for potential participants. At both sites, recruitment may be by informational flyers placed at the recruitment venues and/or by physicians at those venues discussing possible participation in this study with potential participants. Patients identified through EMR review may be approached via opt-out mailing sent on behalf of their primary physician. If subjects do not opt-out they will be contacted by study staff.

Recruitment strategies. It is not anticipated that additional recruitment methods or strategies will be needed to achieve our planned target enrollment within one year.

Participant retention. Given the short participation period for each participant (i.e., about a week or less to complete both imaging visits), it is not anticipated that participant retention will be a problem in this study.

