7.3 LOST TO FOLLOW-UP

A participant will be considered lost to follow-up if he or she fails to return for Visit 1 and/or Visit 2, and is unable to be contacted by the study site staff.

The following actions must be taken if a participant fails to return to the clinic for a required study visit:

- The site will attempt to contact the participant and reschedule the missed visit within the specified time frame and counsel the participant on the importance of maintaining the assigned visit schedule and ascertain if the participant wishes to and/or should continue in the study.
- Should the participant continue to be unreachable, he or she will be considered to have withdrawn from the study with a primary reason of lost to follow-up.

If a participant is lost to follow-up and has only completed one study visit, they may or may not be replaced as part of the targeted enrollment. This decision will be based on the number of subjects who have completed the study to date.

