9.3 POPULATIONS FOR ANALYSES

All participants completing Visit 1 and Visit 2 with evaluable ultrasound images as defined during central review will be included in the analysis.

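### Section 9.2's 25% loss allowance would leave 30 VCTE pairs against its own 32, and that 32 and the table's 40 fit different 95% bounds

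*Combined protocol and SAP*

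**What the plan says.** Section 9.2 sizes the two primary objectives separately. For pooled ultrasound, its table, headed "Number of Independent Observations needed for" at least 80% power, gives 40, 45, 50 and 55 observations for four sets of scanner RDCs. The 40 is for all five scanners at 25%. The 55 becomes 28 participants through a design effect of 1.5 and three scanners per participant. For VCTE, with a true RDC of 25%, "32 subjects provides 80% power to show that the" RDC is below 35%. Enrolment follows directly: "Taking into consideration the possibility of a drop-out or technical failure rate of no more than 25%, a study with 40 total participants" is proposed, 20 per site.

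The synopsis places losses inside the 40: "Dropouts and technical failures were included in this sample size determination". Section 9.3 defines the analysis set: "All participants completing Visit 1 and Visit 2 with evaluable ultrasound images as defined during central review will be included in the analysis". Under section 4.1, at Visit 1 "the third ultrasound exam and the VCTE exam will be performed once", and VCTE is repeated at Visit 2, so each participant gives one different-day VCTE pair. Section 7.3 says of participants lost to follow-up after one visit that "they may or may not be replaced as part of the targeted enrollment", depending on how many have completed.

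The success limit is worded in two ways. The synopsis and section 4.1 refer to the upper limit of a 95% confidence interval. Sections 9.2 and 9.4.2 refer to an upper 95% confidence bound, although the simulation in 9.2 and the bootstrap in 9.4.2 also mention a 95% CI.

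**The concern.** A stated loss ceiling should leave the stated requirement intact. For VCTE it does not, if the 25% is read in the ordinary way as a share of those enrolled and is applied to VCTE pairs.

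The second mismatch matters more. One section gives 32 and 40 for what is, for independent pairs, the same problem: true RDC 25%, limit 35%, 80% power. If the two numbers come from different bounds, the plan has not settled which bound decides whether a biomarker meets the 35% criterion. That choice moves VCTE power at 32 pairs by about 12 percentage points.

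**Working it through.** **Inputs.** From 9.2: VCTE requirement 32; true RDC 25%; limit 35%; loss up to 25%; enrolment 40; pooled requirement 55 observations, design effect 1.5, three scanners per participant. From 9.4.2: the estimator and the bound RDC × √(N/q).

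**Assumptions.** VCTE uses the 9.4.2 estimator with one device and N pairs. The percentile q is taken from the lower tail of chi-square with N degrees of freedom: the 5th for a one-sided 95% bound, the 2.5th for the upper limit of a two-sided 95% CI. (9.4.2 writes α as 0.95, but an upper-tail percentile would not give an upper bound.)

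**Loss arithmetic.**
- 40 × 0.75 = 30, against 32.
- 40 × 0.80 = 32, so the largest VCTE loss covered is 1 − 32/40 = 20%.
- 32/0.75 = 42.7, so 43 would be needed at 25% loss. The 40 equals 32 × 1.25.
- Pooled ultrasound: 55 × 1.5/3 = 27.5, so 28, and 1 − 28/40 = 30% loss is covered. At 25% loss, 30 × 3/1.5 = 60 effective observations against 55.

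**Reproducing the plan's sizes.** Pairs were simulated as normal with mean 1 and wCV = RDC/2.77 (25/2.77 = 9.0%), 200,000 runs. With a constant wCV the estimator does not depend on the mean, so the value 1 is only a scale.

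| Table entry | N | Two-sided 95% CI | One-sided 95% bound |
|---|---|---|---|
| all 25% | 40 | 80.0% | 89.0% |
| 24, 25, 25, 26, 27% | 45 | 80.6% | 89.3% |
| 23, 25, 25, 27, 29% | 50 | 80.1% | 88.8% |
| 23, 25, 25, 27, 30% | 55 | 81.7% | 89.8% |

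All four table sizes fit the two-sided CI.

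For VCTE there is also an exact form. N × (estimated RDC)²/(true RDC)² is approximately chi-square on N degrees of freedom, so power = P(χ²_N < (35/25)² × q) = P(χ²_N < 1.96 q).

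| VCTE pairs | One-sided, simulated (exact) | Two-sided, simulated (exact) |
|---|---|---|
| 30 | 78.4% (80.0%) | 65.6% (67.4%) |
| 32 | 81.0% (82.6%) | 69.0% (70.7%) |
| 40 | 89.0% (90.3%) | 79.9% (81.7%) |

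One-sided simulated power is 79.6% at 31 pairs, so 32 is the first size to reach 80%, which reproduces the plan's figure. On the two-sided CI about 40 pairs are needed (39 by the exact form, 80.5%). The 32 therefore fits only the one-sided bound.

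**Where losses are counted.** Section 5.5 counts "loss of participants due to possible uneven filling of our three enrollment categories, dropout, and technical failure" in its effective screen-fail rate of up to about 25%, which takes 50 screened to 40 enrolled. The synopsis and 9.2 count dropout and technical failure within the 40.

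**The case against.** The 25% is a ceiling, not an expectation. Section 5.5 foresees no retention problem, with both visits done in about a week. VCTE is repeated at Visit 2, so one failed reading there need not lose the pair. The plan gives a single combined rate and none for VCTE, so VCTE loss may well be lower. Replacement under 7.3 is tied to the number who have completed, so it can respond to a shortfall. All of this stands, and it is why the shortfall is conditional. It does not make 30 equal 32. Replacement is optional, and 7.3 does not address technical failures.

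The 25% may also have been meant as an add-on to the target. Both 32 × 1.25 = 40 and, in 5.5, 40 × 1.25 = 50 fit that pattern. If so, only the word for the rate is wrong, and 20% of those enrolled is the same allowance stated properly. That is plausible, but 9.2 does not say it.

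On sidedness, 9.4.2 uses a single percentile and a 95% upper bound, which favours a one-sided rule. Under that rule the 66–71% powers and the absent margin do not arise. The synopsis and 4.1 point the other way, and the table's sizes fit a two-sided interval. Which convention lies behind each number is inferred from fit; the documents do not state it.

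A reader might infer that VCTE is underpowered, or that enrolment must rise to 43. The documents do not support either. On the one-sided bound, 40 evaluable pairs give about 89–90% power, and even the 25% ceiling costs at most about 2 points against the 80% target. Nothing in the documents indicates that VCTE loss will reach 25%.

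**Conclusion.** The concern holds in limited form, and its severity is minor. By the plan's own figures, 40 enrolled cover at most 20% VCTE loss, not 25%. On the one-sided bound behind the 32, the consequence is 0 to 2 points below 80% power. It arises only if unreplaced VCTE loss is 9 or 10 of 40.

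The more substantive defect is that the 32 and the table's 40 cannot both follow from one convention, and the wording of the criterion is split in the same way. If the two-sided CI governs, 40 enrolled leave essentially no loss margin for VCTE. Pooled ultrasound is unaffected by the 25% allowance on either convention, so the point does not extend to the study's overall size.

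The loss arithmetic assumes that the combined rate applies to VCTE pairs. The power figures assume normal pairs, a constant wCV and a true RDC of 25%.

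**What to change.** First, state one convention, either a one-sided 95% upper bound or the upper limit of the two-sided 95% CI. Use it for both primary objectives and for the decision rule in 9.4.2, and align the synopsis and 4.1 with it. Only then restate the loss allowance and power in 9.2:

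- **If one-sided:** VCTE needs 32 evaluable pairs; 40 enrolled cover up to 20% VCTE loss; power at 25% loss is about 78–80%; and the pooled table sizes are conservative, at about 89–90% power.
- **If two-sided:** VCTE needs about 40 evaluable pairs; 40 enrolled leave essentially no loss margin; VCTE power is about 69–71% at 32 pairs and 66–67% at 30; and the pooled requirement of 28 still tolerates up to 30% loss.

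Optionally, align 5.5 with 9.2 and the synopsis on whether dropout and technical failure come out of the 50 screened or the 40 enrolled.

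The cost is wording only. Enrolment and visits do not change. The price is a smaller stated VCTE loss margin: 20%, or about none on the two-sided convention.

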9.3 POPULATIONS FOR ANALYSES

All participants completing Visit 1 and Visit 2 with evaluable ultrasound images as defined during central review will be included in the analysis.

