4.2 SCIENTIFIC RATIONALE FOR STUDY DESIGN

All study participants will be scanned on a subset of ultrasound-based scanners. All study participants will contribute data to the primary and secondary outcomes while minimizing burden on the patient.

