4.4 END OF STUDY DEFINITION

A participant will be considered to have completed this study if:

- all scheduled Visit 1 and Visit 2 ultrasound exams have been performed, and
- all requested demographic, history, vital signs, and anthropometric information have been collected.
- blood has been collected to measure the needed laboratory values

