7 STUDY INTERVENTION

7.1 DISCONTINUATION OF STUDY INTERVENTION

If participants become intolerant to ultrasound scanning they may discontinue. If they have not completed Visit 2 they will be withdrawn from the study.

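### Section 9.3 applies one both-visits analysis set to every endpoint, which excludes Visit 1 same-day data that the secondary coefficients could use

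*Combined protocol and SAP*

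**What the plan says.** Section 9.3 is the only analysis-set rule: "All participants completing Visit 1 and Visit 2 with evaluable ultrasound images as defined during central review will be included in the analysis". It names no endpoint and no scanner, so the same set serves the primary, secondary and exploratory coefficients.

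Other sections bear on it:

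- **Section 4.1** sets the exam layout. Each participant is scanned on three of the five ultrasound systems plus VCTE. At Visit 1, "two of the three ultrasound exams will be repeated; the third ultrasound exam and the VCTE exam will be performed once". At Visit 2, the third ultrasound exam and VCTE are repeated.
- **Section 4.4** counts a participant as complete when, among other things, "all scheduled Visit 1 and Visit 2 ultrasound exams have been performed, and" the clinical data and blood have been obtained.
- **Section 7.1**, on participants who cannot tolerate scanning, says: "If they have not completed Visit 2 they will be withdrawn from the study". It does not say whether their Visit 1 data are kept.
- **Section 7.3** leaves replacement to discretion. Its wording for a person who can no longer be reached and has attended once is: "has only completed one study visit, they may or may not be replaced as part of the targeted enrollment". It is also silent on the data already collected.
- **Section 4.2** says, as design rationale: "All study participants will contribute data to the primary and secondary outcomes while minimizing burden on the patient".
- **Sections 9.4.2 and 9.4.3** build every coefficient from pairs of readings, with counts per scanner, per pair of scanners, or over all observations.

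**The concern.** The unit of inclusion does not match the unit of analysis. Each coefficient is a sum over pairs of readings, while inclusion is decided once per participant and requires both visits.

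Two secondary coefficients, same-day repeatability and same-day different-scanner reproducibility, use readings from a single visit. A participant with a complete Visit 1 and no Visit 2 has two finished ultrasound repeat pairs and three same-day comparisons between scanners. Nothing needed for those quantities is missing, yet the rule leaves them out. What is at stake is some precision in secondary results.

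There is also a gap. With 12 exams per participant on four devices, an isolated failed exam is foreseeable, and Section 9.2 itself allows for technical failure. Section 9.3 does not say whether such a participant keeps the remaining usable pairs. That choice touches both primary endpoints and should be fixed before central review results are known.

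**Working it through.** **Inputs.** 40 participants, a drop-out or technical-failure allowance of up to 25%, 55 independent observations needed, r = 0.25, and 32 participants for VCTE (Section 9.2). Exam layout from Section 4.1. Bound form: coefficient × √(N / χ² percentile) (Sections 9.4.2 and 9.4.3).

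**The plan's own figure.** Design effect 1 + (3 − 1) × 0.25 = 1.5, and 55 × 1.5 / 3 = 27.5, giving 28 participants. This reproduces.

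**Planned pairs with 40 participants.**

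- Different-day ultrasound pairs: 40 × 3 = 120.
- Same-day ultrasound repeats: 40 × 2 = 80 at Visit 1 and 40 × 1 = 40 at Visit 2, together 120.
- VCTE repeats: 40, all at Visit 2.

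**If 10 of 40 attend Visit 1 only** (the whole 25% allowance, taken as the extreme case):

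| Quantity | Section 9.3 as written | Inclusion by pair |
|---|---|---|
| Same-day ultrasound repeats | 30 × 3 = 90 | 30 × 3 + 10 × 2 = 110 |
| Same-day scanner comparisons from the 10 | 0 | 10 × 3 = 30 |
| Different-day ultrasound pairs | 90 | 90 |
| VCTE repeats | 30 | 30 |

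The repeat pairs lost are 20 of 110, or 18%. I use the lower 5th percentile for the bound, because the 95th percentile would put it below the estimate. I also treat pairs as independent, as the formula does.

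- N = 90: √(90 / 69.126) = 1.141.
- N = 110: √(110 / 86.792) = 1.126.

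The bound is therefore just over 1% wider. With smaller Visit-1-only losses of 5% or 10% (2 or 4 participants), 4 or 8 repeat pairs are dropped.

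These counts pool repeats from both visits, since Section 4.1 plans repeats at both. The definition in Section 9.4.3 mentions timepoint 1 only. Taken literally, the comparison would be 30 × 2 = 60 against 40 × 2 = 80.

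**Pooled primary endpoint.** A participant without Visit 2 has no different-day pair under any rule. With 30 participants left, 90 / 1.5 = 60 effective observations, above the 55 needed.

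**Partly evaluable participants.** The documents give no exam failure rate, so the rates here are assumptions. Suppose one failure among 12 independent exams removed the participant from every analysis. VCTE power is one-sided at an RDC of 25%: P(χ²_N < 1.96 × χ²_{N,0.05}), where 1.96 = (35/25)².

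| Assumed failure per exam | Participants kept, strict reading | VCTE n and power, strict | VCTE n and power, by pair |
|---|---|---|---|
| 3% | 0.97¹² = 69% | 28, 77% | 40 × 0.97² ≈ 37, 88% |
| 5% | 0.95¹² = 54% | 22, 66% | 40 × 0.95² ≈ 36, 87% |

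Alternatively, assume each of the four device pairs fails independently with probability 10%. The strict reading keeps 40 × 0.9⁴ = 26.2 participants, giving 3 × 26.2 / 1.5 = 52.5 effective ultrasound observations. Inclusion by pair keeps 120 × 0.9 / 1.5 = 72, and 36 for VCTE.

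**The case against.** **The strict reading is not written.** A reader might infer that one failed exam removes all of a participant's other scanner pairs. Section 9.3 does not say that all images must be evaluable. The definition of a completed participant in Section 4.4 would support that inference, but Section 9.3 does not refer to it. The per-scanner and per-scanner-pair counts in Sections 9.4.2 and 9.4.3 are compatible with keeping every usable pair. Evaluability is left to central review, and the separate Image Review Charter may settle it. This stands: the rule for partly evaluable participants is undefined, which is less than saying that usable pairs are discarded.

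**The primary-endpoint loss needs rates beyond the plan's allowance.** Failure rates of 3% and 5% per exam imply losing 31% and 46% of participants, against the 25% in Section 9.2. At 25% loss, 30 participants remain and the same formula gives 80% power for VCTE. The 12-exam model also ignores that VCTE is read twice at Visit 2, so one failed reading need not break the different-day pair. This stands too.

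**VCTE falling below 32.** A reader might attribute this to Section 9.3. A 25% loss from 40 leaves 30 whatever the analysis set says, so the attribution fails for participants who miss Visit 2.

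**Conflict with Section 4.2.** A reader might see a contradiction with "All study participants will contribute data to the primary and secondary outcomes". That sentence explains why each participant is scanned on a subset of the systems. It is not an analysis rule, and it could not hold for someone who misses Visit 2. There is a tension in wording only.

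**The certain loss is small.** Section 5.5 expects no retention problem, Section 7.3 allows replacement, and the 35% criterion applies to the primary coefficients, so no stated decision changes. This limits the severity. It does not justify excluding complete pairs.

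**Conclusion.** The point holds in a limited form. Followed as written, Section 9.3 excludes the Visit 1 same-day ultrasound repeats and different-scanner comparisons of anyone who misses Visit 2, although those coefficients need one visit only. The most this can cost within the plan's allowance is 20 of 110 repeat pairs and 30 scanner comparisons, with a bound multiplier of 1.141 in place of 1.126. That figure assumes the entire 25% is Visit-1-only loss without replacement.

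Neither primary endpoint, nor VCTE repeatability, loses anything through this exclusion. Separately, the handling of participants with some non-evaluable exams is undefined. A loss of usable primary pairs would require the strict reading, and its size rests on failure rates that the documents do not give.

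Severity: minor, a cheap improvement.

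**What to change.** Replace Section 9.3 with inclusion defined by coefficient and by participant-scanner pair:

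- **Same-day coefficients** use every pair of evaluable readings obtained at the same visit, including those of participants with one visit only.
- **Different-day coefficients** use each ultrasound scanner, and the VCTE device, with an evaluable reading at both visits.
- **A non-evaluable exam** removes only the pairs that depend on it.
- **Reporting:** give N for each coefficient, and list the excluded pairs with reasons.

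The text should be settled before central review results are available, and checked against the Image Review Charter so that evaluability is judged per exam.

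The cost is a short rewrite of one section. The downside is that N will differ between coefficients, so each table must show its own. The estimators in Sections 9.4.2 and 9.4.3 already count per scanner, per scanner pair or per observation, so they need no change for this purpose.
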